## 1 INTRODUCTION

This statistical analysis plan (SAP) is based on the protocol TT-TSND-201 of Transcend Therapeutics, ‘A Pilot Study to Assess the Use of Methylone in the Treatment of PTSD IMPACT-1 (Investigation of Methylone for Post-Traumatic Stress Disorder [PTSD])’. This SAP is used for Part B of protocol TT-TSND-201.

The purpose of this SAP is to outline in detail the statistical methods, data derivations, method for handling missing data, definition of analysis population and presentations of data. Specifications for tables, figures, and listings are contained in a separate document. Unless otherwise stated with reasoning, the methods discussed in this SAP are the ones outlined in the Protocol.

This SAP is written in compliance with the ICH E3 (Structure and Content of Clinical Study Reports) and ICH E9 (Statistical Principles for Clinical Trials) published by the International Coordination of Technical Requirements for the Registration of Human Drugs (ICH).

## 2 STUDY OBJECTIVES

### 2.1 Primary Objective

The primary objective of this study is to assess the efficacy of methylone in treating PTSD symptoms.

### 2.2 Secondary Objectives

The secondary objectives of this study are as follows:

- To assess the effect of methylone compared to placebo on sleep quality, functional disability, treatment satisfaction, quality of life, and physical function in participants with PTSD.
- To assess the safety and tolerability of oral methylone compared to placebo administered weekly over 4 weeks in participants with PTSD.

## 3 STUDY DESIGN

### 3.1 Study Design Overview

This is a two-part study to assess methylone for the management of the symptoms of PTSD. Part A was an open-label, non-controlled assessment in approximately 15 evaluable participants with PTSD to assess early safety and efficacy and to confirm procedures included in the blinded portion (Part B) of the study. After completion of Part A, enrollment for Part B began. Unless otherwise stated, Part B is identical to Part A with the exception of the inclusion of a placebo arm in Part B. This SAP covers the analysis of the Part B data.

Part B is a randomized, double-blind, parallel-group, placebo-controlled assessment of methylone for the management of the symptoms of PTSD in approximately 64 patients. This multi-center study will be conducted in up to 25 sites globally.

There are 4 planned dose sessions for each participant. Participants in Part B will be randomized 1:1 to the one of the two study treatment arms and will receive treatment at each of the weekly dose sessions for the duration of the study.

The two blinded study treatment arms for Part B are:

- Methylone 150 mg, with a booster administration of 100 mg administered 90 ( $\pm$ 10) minutes after the initial administration, during each dose session.
- Matched placebo at each timepoint (initial + booster) during each dose session.

For each participant the study consists of:

- **Screening Period (Day -28 to Baseline):** Informed consent, eligibility assessment, and enrolment of eligible participants.
- **Baseline/Preparatory Session (Day -4 to Day -1):** Baseline assessments, confirmation of eligibility, and a preparatory psychoeducation session leading to enrolment confirmation.
- **Treatment Period (Day 1 to Day 24):** Four weekly dose sessions. Each dose session is followed by a safety phone call 1 day after dosing and efficacy assessments 2 days after dosing.
- **Follow-Up Period (Day 29 to Day 64):** Follow-Up visits for efficacy and safety will occur at 1, 2, 3 and 6 weeks post-final study drug administration..

The expected duration of participation for each participant who completes all study visits, from Screening to the EOS visit, is up to 16 weeks.

Screening (Up to 28 days)		Treatment Period (4 weeks) (methylone [Part A]; methylone or placebo [Part B])												Follow-up (6 Weeks)				
Day -28 to Baseline		Treatment #1			Treatment #2			Treatment #3			Treatment #4			Day 29	Day 36	Day 43	Day 57	Day 64
Screening visit	Baseline / Preparatory Session	Day 1	Day 2	Day 3	Day 8	Day 9	Day 10	Day 15	Day 16	Day 17	Day 22	Day 23	Day 24	Efficacy / Safety / Reflect session	Efficacy / Safety / Reflect session	Efficacy / Safety / Reflect session	Phone visit: Safety	Efficacy / Safety Assessments
		In-clinic: Dose Session	Phone visit: Safety	Efficacy / Safety Assessments	In-clinic: Dose Session	Phone visit: Safety	Efficacy / Safety Assessments	In-clinic: Dose Session	Phone visit: Safety	Efficacy / Safety Assessments	In-clinic: Dose Session	Phone visit: Safety	Efficacy / Safety Assessments					

## 4 SAMPLE SIZE DETERMINATION

Sample size calculations for Part B were performed using PASS 2022 to determine the sample size required to detect a significant difference between CAPS-5 scores in the methylone and placebo groups (the efficacy endpoint). A previous phase 3 trial investigating the effects of MDMA versus placebo on CAPS-5 scores found a placebo-corrected treatment effect at the end of treatment of 11 points and a pooled standard deviation (SD) of 12 (Mitchell 2021). Assuming a treatment effect of 11 points and a pooled SD of 12 in this trial, with a sample size of 20 or 27 evaluable participants in each treatment group, the trial should provide 80% or 90% power, respectively. Assuming a dropout rate of 15%, a target sample size of 46 (23 per treatment group) or 64 (32 per treatment group) will provide 80% or 90% power, respectively.

## 5 ANALYSIS SETS

### 5.1 Modified Intent-to-Treat (mITT) Population

The mITT population includes all participants who are randomized, received at least 1 dose of study drug and have at least 1 valid post-baseline assessment. Participants are analyzed on the treatment to which they are randomized to receive.

### 5.2 Per-Protocol Population

The Per-Protocol population includes all participants in the mITT population who received at least one administration of study treatment and have no important protocol deviations.

### **5.3 Safety Population**

The Safety population includes all participants who receive at least one administration of study treatment. Participants will be summarized according to treatment received. The Safety population will be used to analyze the safety endpoints.

## **6 ENDPOINTS AND COVARIATES**

### **6.1 Efficacy Assessments**

#### **6.1.1 Clinician-Administered PTSD Scale for DSM-5 (CAPS-5)**

The CAPS-5 is a 30-item structured interview that can be used to: Make a current diagnosis of PTSD; Assess change in PTSD symptoms over time.

In addition to assessing the 20 DSM-5 PTSD symptoms, questions target the onset and duration of symptoms, subjective distress, impact of symptoms on social and occupational functioning, improvement in symptoms since a previous CAPS administration, overall response validity, overall PTSD severity and specifications for the dissociative subtype (depersonalization and derealization). The CAPS-5 also rates intrusion symptoms (intrusive thoughts or memories), avoidance, cognitive and mood symptoms, arousal and reactivity symptoms, duration and degree of distress.

The CAPS-5 total severity score (primary efficacy measure) is calculated by summing severity scores for items 1-20. CAPS-5 severity scores range from 0-80 points, with higher scores indicating greater PTSD symptom severity.

The CAPS-5 symptom cluster severity scores are calculated by summing the individual item severity scores for symptoms contained in a given DSM-5 cluster. Thus, the Criterion B (intrusion) severity score is the sum of the individual severity scores for items 1-5; the Criterion C (avoidance) severity score is the sum of items 6 and 7; the Criterion D (cognitions and mood) severity score is the sum of items 8-14; and the Criterion E (arousal and reactivity) severity score is the sum of items 15-20. A symptom cluster score may also be calculated for dissociation by summing items 29 and 30.

PTSD diagnostic status is determined on the CAPS-5 by first dichotomizing individual symptoms as “present” or “absent” then following the DSM-5 diagnostic rule. A symptom is considered present only if the corresponding item severity score is rated 2=Moderate/threshold or higher otherwise a symptom is considered absent. The DSM-5 diagnostic rule requires the presence of least one Criterion B symptom, one Criterion C symptom, two Criterion D symptoms, and two Criterion E symptoms. Criterion G requires a rating of 2=moderate or higher on items 23-25.

#### **6.1.2 Structured Interview Guide for the Montgomery-Åsberg Depression Rating Scale (MADRS) (SIGMA)**

The SIGMA is a standardized version of the MADRS. The SIGMA maintains the original format of the MADRS, which is a 10-item clinician-rated, diagnostic questionnaire used to measure depression severity, with the exception that the first two items are reversed. Each item is measured on a 7-point scale, from 0 to 6. Higher total MADRS scores indicate more severe depression. Follow-up questions are also provided to clarify symptoms, if required.

Total MADRS score ranges from 0-60 points, with higher total scores indicating more severe depression.

#### **6.1.3 Clinician Global Impressions Scale – Severity (CGI-S)**

The CGI-S is designed to acquaint the participant’s severity of symptoms with those of other people experiencing the same mental ailment. The CGI-S rates this severity on a 7-point scale,

with (1) representing normal symptoms, meaning the participant is not ill, and (7) representing participants among the most severely ill. The rating (4) represents a participant that is defined as a participant that is defined as moderately ill.

#### **6.1.4 Sheehan Disability Scale (SDS)**

The SDS is a brief, 5-item self-report tool that assesses functional impairment in work, social life/leisure activities and family life/home responsibilities. The SDS is designed to measure the extent to which the three major domains in the participant's life are functionally impaired by psychiatric or medical symptoms. Each domain is rated from 0 to 10, with higher scores representing more functional impairment. The total score is the mean of the domains.

In addition, the SDS also collects information on the number of days lost and underproductive during the past week.

#### **6.1.5 PTSD Checklist for DSM-5 (PCL-5)**

The PCL-5 is a 20 item self-report measure that assesses the presence and severity of the 20 DSM-5 symptoms of PTSD. Participants rate each item from 0 ('not at all') to 4 ('extremely') to indicate the degree to which they have been affected by that particular symptom over the past week.

A total symptom severity score ranges from 0 to 80, with higher scores representing more severe symptoms.

#### **6.1.6 Patient Global Impression of Severity (PGI-S)**

The PGI-S is a self-report tool to measure disease severity. The PGI-S is a 5-point scale, ranging from '1 – None', through to '5 – Very severe'.

#### **6.1.7 Beck Depression Inventory-II (BDI-II)**

The BDI-II is a 21-item self-report measure assessing depressive symptoms and their severity. Items include hopelessness and irritability, cognitions such as guilt or feelings of being punished, as well as physical symptoms such as fatigue and weight loss. Each item is rated on a 4-point scale, from 0 to 3. Items are summed to create a total score.

A total score ranging from 0 to 63 is possible, with higher scores indicating higher levels of depression.

#### **6.1.8 Warwick-Edinburgh Mental Wellbeing Scale (WEMWBS)**

The WEMWBS is a scale of 14 positively worded items for assessing a population's mental wellbeing. The items cover both physiological functioning aspects of mental wellbeing (including: optimism, autonomy, agency, curiosity, clarity of thought and positive relationships) and positive effect (feelings, including: confidence, feeling relaxed, cheerful, having the energy to spare). The scale has 5 response categories, ranging from 1 "none of the time" to 5 "all of the time", summed to provide a single score.

A total score ranging from 14 to 70 is possible, with higher scores indicating higher levels of mental wellbeing.

#### **6.1.9 Pittsburgh Sleep Quality Index (PSQI)**

The PSQI is a measure of self-reported sleep quality and sleep disturbance. The PSQI contains 19 self-rated questions, which are combined to form 7 'component' scores, each of which has a range of 0 to 3 points. The 7 components of the PSQI are: subjective sleep quality, sleep latency, sleep duration, habitual sleep efficiency, sleep disturbances, use of sleeping medications and daytime dysfunction.

The sleep component scores are summed to yield a total score ranging from 0 to 21, with a higher total score indicating worse sleep quality.

See [Appendix 1 Scoring Instructions for the PSQI](#).

#### 6.1.10 Patient Global Impression of Change (PGI-C)

The PGI-C is a self-report tool to reflect a participant’s belief about the efficacy of treatment. The PGI-C is a 7-point scale depicting a participant’s rating of overall improvement. Participants rate their change from ‘1 – Very much improved’ through to ‘7 – Very much worse’.

#### 6.1.11 Clinician Global Impressions Scale – Improvement (CGI-I)

The CGI-I is a 7-point scale that requires the assessor to assess how much the participant’s illness has improved or worsened relative to a baseline state prior to dosing. The CGI-I scale rates improvement with (1) representing a ‘very much improved’ participant to (7) representing a participant who has become ‘very much worse’ due to treatment. The rating (4) represents a participant displaying no change from the treatment.

#### 6.1.12 Post-Traumatic Growth Inventory (PTGI)

[figure not shown]
The Post-Traumatic Growth Inventory measures the extent to which survivors of traumatic events perceive personal benefits, including changes in perceptions of self, relationships with others and philosophy of life, accruing from their attempts to cope with trauma and its aftermath.

This 21-item scale includes factors of: new possibilities, relating to others, personal strength, spiritual change and appreciation of life.

The PTGI is scored by adding the individual responses (ranging from 0 “I did not experience this change as a result of my crisis” to 5 “I experienced this change to a very great degree as a result of my crisis”). Total scores range from 0 to 105, with higher scores indicating that the person has undergone a positive transformation. Individual factors are scored by adding responses to items on each factor.

Factor	Item Numbers
Factor I: Relating to Others (0 to 35)	Q6; Q8; Q9; Q15; Q16; Q20; Q21
Factor II: New Possibilities (0 to 25)	Q3; Q7; Q11; Q14; Q17
Factor III: Personal Strength (0 to 20)	Q4; Q10; Q12; Q19
Factor IV: Spiritual Change (0 to 10)	Q5; Q18
Factor V: Appreciation of Life (0 to 15)	Q1; Q2; Q13

[Redacted text block]

[Redacted text block]

[Redacted text block]

[Redacted text block]

[Redacted text block]

[Redacted text block]

**6.1.15 Blinding Integrity Questionnaire (BIQ)**

The BIQ is a visual analogue scale that will be used to ascertain the degree of blinding perceived by the participant; participants will be asked to circle a number from 0 (strongly believe they

received Placebo) to 10 (strongly believe they received active drug) indicating which treatment they believed they were administered during the dose sessions.

## **6.2 Safety Assessments**

### **6.2.1 Adverse events**

#### **6.2.1.1 Adverse Event**

An AE is any untoward medical occurrence in a study participant which either emerges, or worsens from enrolment/randomization, during the clinical study, regardless of its potential relationship to the medicinal product. An AE, therefore, can be any unfavorable or unintended sign, including a clinically significant abnormal laboratory finding, symptom, or disease temporally, whether or not it is considered to be study drug-related.

#### **6.2.1.2 Serious Adverse Events**

A SAE is any untoward medical occurrence that, at any dose:

- Results in death
- Is life-threatening
- Requires hospitalization or prolongation of existing hospitalization
- Results in persistent or significant disability or incapacity
- Is a congenital abnormality or birth defect
- Is an important medical event

#### **6.2.1.3 Adverse Events of Special Interest**

The Sponsor will pay special attention to a subset of AEs; these AEs will be marked in the eCRF with the denotation AESIs whether serious or non-serious. Adverse events of special interest (AESI) include:

- Grade 3 hypertension, SBP  $\geq 160$  mmHg or DBP  $\geq 100$  mmHg, requiring the need for medical intervention with more than one drug or more intensive therapy than previously used.
- Significant cardiovascular events
- AEs related to suicide risk, such as; suicides, suicide attempts, self-injurious behavior associated with suicidal ideation and suicidal ideation judged to be serious or severe in the opinion of the Investigator.
- Signals of abuse potential AE involving terms of behavioral addiction, drug abuser, substance abuser.

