### Randomized Double-Blind Phase 1 Clinical Trial

A randomized, double-blind, placebo-controlled, cross-over study was conducted to evaluate the pharmacokinetic and subjective experiences in 29 healthy volunteers. The study was divided into two parts, a methylone dose-range finding study in 12 healthy volunteers (Poyatos 2022), followed by a study evaluating 200 mg methylone, 100 mg MDMA, and placebo in 17 healthy volunteers (Poyatos 2023).

Each subject participated in a total of 3 sessions during which they received single oral doses of study drug, each separated by 1 week. In Part 1 three methylone dose escalation cohorts and one MDMA comparison was evaluated:

- 50 mg, 100 mg, placebo (n=3)
- 100 mg, 150 mg, placebo (n=2)
- 150 mg, 200 mg, placebo (n=4)
- 200 mg methylone, 100 mg MDMA, placebo (n=3)

In Part 2, all subjects (n=17) received 200 mg methylone, 100 mg MDMA, and placebo. A 200 mg methylone dose was selected because it evoked similar subjective effects to the 100 mg dose of MDMA (e.g., high or liking feelings), which is considered a common dose used in previous pharmacological studies.

Study outcome measures included pharmacokinetic parameters of methylone, MDMA, and their respective metabolites, subjective effects (eg, VAS, ACRI, and VESSPA), physiological effects (SBP, DPB, HR), and drug tolerability. All subjects completed the methylone doses without any serious adverse effects, including psychiatric symptoms, psychotic episodes, or hallucinations.

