**Table 2: Objectives and Endpoints for Part B**

Objectives	Endpoints
Primary	
To assess the efficacy of methylone in treating PTSD symptoms.	Mean change from baseline to Week 10 compared with placebo in CAPS-5 total severity score.
Secondary	
To assess the effect of methylone compared to placebo on sleep quality, functional disability, treatment satisfaction, quality of life, and physical function in participants with PTSD.	
Mean change from baseline compared with placebo in the following scales:
 
 
• CGI-S
 
• MADRS
 
• SDS
 
• PCL-5
 
• PGI-S
 
• BDI-II
 
• WEMWBS
 
• PSQI
 
 
Percentage of participants with:
 
 
• Treatment response, defined as a 
 
○ <math>\geq 10</math> point reduction on the CAPS-5 from baseline
 
○ 30% improvement from baseline on CAPS-5
 
○ 50% improvement from baseline on CAPS-5
 
 
 
• Remission, defined as a score of <math>\leq 11</math> on the CAPS-5
 
• Improvement on the PGI-C
 
• Improvement on the CGI-I
 

To assess the safety and tolerability of oral methylone compared to placebo administered weekly over 4 weeks in participants with PTSD.	
 
• Incidence and severity of TEAEs
 
• Incidence and severity of AESIs
 
• Change in HR, SBP, DBP and temperature during each dosing session
 
• Clinically significant changes in ECG
 
• Changes from baseline in clinical laboratory parameters (clinical chemistry, hematology, and urinalysis)
 

[REDACTED]	
Effect of the following scales, compared with placebo:
 
 
• PTGI
 
• [REDACTED]
 
• [REDACTED]
 

Abbreviations: [REDACTED] AE = adverse event; AESI = adverse event of special interest; BDI-II = Beck Depression Inventory-II; DBP = diastolic blood pressure; CAPS-5 = Clinician-Administered PTSD Scale for DSM-5; CGI-I = Clinician Global Impression of Improvement; CGI-S = Clinical Global Impression of Severity; C-SSRS = Columbia Suicide Severity Rating Scale; DBP = diastolic blood pressure; ECG = electrocardiogram; HR = heart rate; LEC-5 = Life Events Checklist for DSM-5; MADRS = Montgomery-Åsberg Depression Rating Scale; [REDACTED] MINI = Mini International Neuropsychiatric Interview; PCL-5 = PTSD

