### **5.7 Assessment of Compliance with Treatment**

All doses will be administered by study staff under direct observation. The administration of the study drug will be recorded within the appropriate pages of the eCRF. Any deviations from the planned dosing procedure will be recorded within the eCRF.

Incorrect dosing will be recorded in the eCRF and reported to the Sponsor or delegate within 48 hours. During this study, any initial administration of methylone greater than 150 mg (>3 capsules), and any booster administration of methylone greater than 100 mg (>2 capsules) will be considered an overdose. In the event of an overdose, the Investigator should:

- Evaluate the participant to determine, in consultation with the Medical Monitor, whether study drug administration should be interrupted (ie, hold the booster dose) or if the booster dose should be reduced.
- Document the quantity of the excess dose.

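### The abuse-potential AESI names only addiction and abuser terms, so it will probably show few or no events, and the euphoria-type effects the protocol documents are not grouped as abuse-related

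*SAP*

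**What the plan says.** Protocol Table 2 lists "Incidence and severity of AESIs" among the Part B safety endpoints. SAP 6.2.1.3 opens its definition with "Adverse events of special interest (AESI) include" and then gives four categories:

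- hypertension of Grade 3 that needs stepped-up medical treatment
- cardiovascular events of significance
- events bearing on suicide risk, from attempts to ideation that the investigator judges serious or severe
- for abuse potential, "Signals of abuse potential AE involving terms of behavioral addiction, drug abuser, substance abuser"

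Protocol 7.7.1.3 words the fourth category identically. Neither document, as far as it is visible, adds a MedDRA query or preferred-term list to it.

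On exposure, Protocol 5.7 says "All doses will be administered by study staff under direct observation", and SAP 3.1 plans four dose sessions. Exclusion criterion 3 in Protocol 6.2 removes people with moderate or severe substance use disorder, known abuse of illegal drugs, or a positive urine test at entry.

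On the drug's acute effects, Protocol 2.4.2 explains that 200 mg was taken forward in Phase 1 because "it evoked similar subjective effects to the 100 mg dose of MDMA (e.g., high or liking feelings"). Its subsection on subjective effects reports dose-dependent increases on euphoria-related scales, with every dose from 100 mg upward separating from placebo.

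**The concern.** The category is labelled as a signal of abuse potential, but its terms describe people who already have an addiction or abuse problem. Study drug is not taken home, so an AE coded to one of these terms would usually concern another substance or behaviour. The acute effects that Protocol 2.4.2 reports for this drug, and that the sponsor itself used to match it to MDMA, fall outside the terms. An AE of euphoric mood would not meet the category as worded.

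What is at stake is interpretation. A zero or near-zero count in this category could be read as reassurance about abuse liability when the category was not built to detect the signal the protocol describes.

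**Working it through.** **Number exposed.** Protocol 9.2 assumes a difference of 11, SD 12 and two-sided alpha 0.05.
- With 27 evaluable per group, a two-sample t-test (noncentral t) has 91.1% power, which agrees with the stated 90%.
- With 15% dropout, 27 / 0.85 = 31.8, rounded up to 32 per group and 64 in total, as stated.
- About 32 participants are therefore planned for methylone.

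**What a zero count would show.** Solve (1 − p)^n = 0.05 for p.
- n = 32: p = 1 − 0.05^(1/32) = 8.9%.
- n = 27: p = 1 − 0.05^(1/27) = 10.5%.

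Either bound applies only to the terms counted. It says nothing about euphoria-type events.

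**How likely a zero count is.** The documents give no rate for any abuse-related event, so the rates below are assumptions. P(at least one) = 1 − (1 − p)^32; expected number = 32p.

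| Assumed rate in the methylone arm | Expected participants | P(at least one) |
|---|---|---|
| Three named terms, 0.1% | 0.03 | 3% |
| Three named terms, 1% | 0.32 | 27% |
| Recorded euphoria-type AEs, 1% | 0.32 | 27% |
| Recorded euphoria-type AEs, 5% | 1.6 | 81% |
| Recorded euphoria-type AEs, 20% | 6.4 | 99.9% |

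At 0.1% to 1% for the named terms, the chance of no event is 97% to 73%.

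**Is the euphoria-type range plausible?** The documents suggest caution about its upper part.
- Protocol 2.4.1 lists the commonest Part A TEAEs (14 participants, same regimen) at 43%, 29%, 21% and 21%. None is euphoria-type. Since 3/14 = 21%, any single such term probably occurred in at most 2/14 = 14%. A group of several terms could be higher.
- Protocol 2.4.2 reports 5 TEAEs in 3 volunteers (21.4%, so a denominator of 14), with no term repeated across volunteers, although the euphoria scales separated from placebo.

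**Where a recorded euphoria-type AE would go.** SAP 8.4.1 tabulates all TEAEs by SOC and PT, and by maximum severity and relationship. For AESIs it visibly plans one overall summary row and a listing, with no row per category. Such an event would be counted under its own preferred term but not identified as abuse-related.

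**Whether it would be recorded.** SAP 6.2.1.1 requires an AE to be untoward. Protocol 7.8 prefers open-ended, non-leading questioning. Neither says how pleasurable drug effects are to be handled.

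**The case against.** Several stronger readings are tempting, and the other side is right to resist them.

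- *The whole AESI endpoint will read near zero.* Not supported. Three other categories feed it, and Protocol 5.6.5 expects rises in blood pressure and heart rate.
- *Euphoria-type effects go uncounted.* Not supported. If recorded as AEs, they are in the SOC and PT tables.
- *The named terms cannot arise.* Too strong. Participants are outpatients followed to Day 64. Protocol 6.2 may allow mild substance use disorder and does not exclude moderate alcohol use disorder in early remission. Drug-seeking that emerges after exposure would be a legitimate signal. However, the special-interest row in SAP 8.4.1 counts TEAEs, so an onset more than 7 days after the last dose is left out of that row unless suspected to be drug-related.
- *A misleading 0 versus 0 line will be published.* No category-level AESI line is visibly planned, and the table shells are in a separate file.
- *Nothing else measures acute effects.* This cannot be asserted. The synopsis mentions assessment of psychedelic effects, and the relevant sections are redacted.

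The list is also introduced by a word that leaves it formally open. That helps little, because no rule then decides which further events qualify. The study is a non-confirmatory pilot with descriptive safety analysis (SAP 8.1.5 and 8.4), which limits the consequences.

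These points narrow the concern, but none of them supplies a prespecified abuse-related grouping.

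**Conclusion.** The point holds for the abuse-potential component alone. As worded, it omits the acute effects that Protocol 2.4.2 reports, and under supervised dosing it is likely to show few or no events. A count of 0/32 would leave a rate of up to 8.9% open for the named terms and would not address euphoria-type events at all. How many events a broader grouping would capture is unknown. Under assumed recording rates of 1% to 20% it would be 0.3 to 6.4 methylone participants, and the documents' own TEAE data do not support the top of that range.

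This is a cheap improvement to reporting. It does not affect the primary analysis or the other AESI categories.

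**What to change.** In SAP 8.4.1, prespecify a MedDRA preferred-term grouping of abuse-related AEs: the three existing terms plus euphoria-type and acute psychoactive terms such as euphoric mood, elevated mood, feeling drunk or high, feeling abnormal, and dissociation. Check the term names against the dictionary version in use and fix the list before unblinding; added later, it would have to be labelled unplanned under SAP section 9.

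Flag the grouping programmatically from coded AE data and report it by arm in its own row, separate from the other AESI categories. Leave the eCRF marking of AESIs and the sponsor-reporting rules in Protocol 7.7.1.3 as they are.

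State in the SAP and the study report that AEs must be untoward and are elicited by open-ended questioning, so a low count is not evidence of low abuse potential. The grouping can only find events that sites record.

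The cost is a term list, one table row and a sentence of interpretation. The downside is a possibly less favourable count in the methylone arm.
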